3.7.2 Part B Intra-subject Dose Escalation

For subjects ages below 6 years enrolled in Part B at 0.025 mg/kg/day dose level, an individual subject's trametinib dose level may be increased up to 0.032 mg/kg/day if this dose is found to be tolerated in Part A extension and if the subject has (all of the following must be true):

- completed at least 56 days of treatment,
- not experienced a drug related toxicity greater than Grade 2,
- met criteria for continuation of study treatment ([Section 3.6](#)),

Subjects who meet criteria for intra-subject dose escalation and receive the higher dose may continue to follow the time and event table using the originally assigned study day 1

Subjects may be allowed to re-escalate following dose reduction for AE upon resolution of AE. Please follow guidelines in [Section 3.13](#).

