3.12.3 Left Ventricular Ejection Fraction (LVEF) and Valvular Toxicity Stopping Criteria

3.12.3.1 LVEF Stopping Criteria

Decreases of the left-ventricular-ejection-fraction (LVEF) have been observed in subjects receiving trametinib monotherapy and in combination with dabrafenib. Therefore, ECHOs must be performed to assess cardiac ejection fraction in regular intervals as outlined in the Time and Events Table ([Section 7.1](#)). Dose modification guidance and stopping criteria for LVEF decrease are provided in [Table 3-5](#).

ECHO should be performed at baseline and at follow up visit(s). Electronic copies of all ECHO scans will be collected by Novartis for review. Instructions for submission of ECHO scans are provided in the Study Procedures Manual (SPM).

Table 3-5 Mandatory dose modification and required clinical management for LVEF

LVEF-drop (%) & clinical symptoms	Required adverse event management guidelines	Mandatory dose modification requirements
Asymptomatic: Absolute decrease of >10% in LVEF compared to baseline and ejection fraction below the institution's LLN	
 • Report as SAE. • Closely monitoring LVEF via ECHO, repeat ECHO within 2 weeks. If ECHO does not show LVEF recovery after 2 weeks, repeat ECHO 2 weeks later • If the LVEF recovers within 4 weeks (defined as LVEF ≥LLN and absolute decrease ≤10% compared to baseline) 
 • Repeat ECHO 2, 4, 8 and 12 weeks after re-start; continue in intervals of 12 weeks thereafter. 	Interrupt trametinib (on combination therapy dabrafenib may continue) If the LVEF recovers within 4 weeks, 
 • restart treatment with trametinib dose reduced to levels indicated in Appendix 2, dose reduction column and continue dabrafenib at the same dose level. • If the event recurs at the reduced dose level, permanently discontinue trametinib. On combination therapy dabrafenib may continue

LVEF-drop (%) & clinical symptoms	Required adverse event management guidelines	Mandatory dose modification requirements

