3.13 Dose Delay and Modification for Events Considered Related to Trametinib

A maximum of one trametinib dose reduction is allowed. If a second dose level reduction is required, treatment will be permanently discontinued.

Trametinib dose modification guidelines are outlined in [Table 3-6](#) for clinically significant toxicities with exception for following events of special interest:

- rash ([Section 3.13.3](#))
- diarrhea ([Section 3.13.4](#))
- ejection fraction changes ([Section 3.12.3.1](#))
- hypertension ([Section 3.13.5](#))
- prolonged QTc ([Section 3.12.1](#))
- pneumonitis ([Section 3.13.5](#))
- visual changes ([Section 3.13.5](#))
- liver chemistry elevation ([Section 3.12.1](#))

For these refer to the relevant sections for dose modification guidelines for adverse events of special interest as stated above.

If treatment related toxicities occur when dabrafenib is used in combination with trametinib then both treatments should be simultaneously dose reduced, interrupted or discontinued with the exceptions described below.

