3.13.1 Dose Delay and Modification for Events Considered Related to Trametinib and/or Dabrafenib

Table 3-6 Dose Delay and Modification for General Events Considered Related to Trametinib and/or Dabrafenib

CTCAE Grade	Recommended adverse event management guidelines	Mandatory dose modification requirements
Grade 1 and tolerable Grade 2	
 • Monitor closely • Provide supporting care according to institutional standards 	
 • Continue study drug(s) at current dose level
Intolerable Grade 2 and Grade 3	
 • Monitor closely. • Provide supportive care according to institutional standards. 	
 • Interrupt study drug(s) (except for cuSCC, keratoacanthoma, new primary melanoma, and basal cell carcinoma) • When toxicity resolves to Grade 1 or baseline, restart study drug(s) at reduced levels (see Appendix 2 dosing nomogram "Dose Reduction" columns for trametinib and dabrafenib) • If the Grade 2 (intolerable) or Grade 3 toxicity recurs while at reduced dose, discontinue study treatment(s) • If the Grade 2 (intolerable) or Grade 3 toxicity recurs while after re-escalating to previous dose,

CTCAE Grade	Recommended adverse event management guidelines	Mandatory dose modification requirements
		
 Interrupt dabrafenib and trametinib. When toxicity resolves to Grade 1 or baseline, restart study drug(s) reduced levels (see Appendix 2 dosing nomogram "Dose Reduction" columns for trametinib and dabrafenib)
Grade 4	
 Monitor closely. Provide supportive care according to institutional standards. 	
 Interrupt study drug (s) Once toxicity resolves to \leq Grade 1 or baseline, restart study drug(s) at reduced levels (see Appendix 2 dosing nomogram "Dose Reduction" columns for trametinib and dabrafenib) or permanently discontinue study drug (s) at the discretion of investigator

Table 3-6a Dose Modification for dabrafenib (DRB436) dispersible tablet for patients less than 12 years of age

Weight (kg)	Dose (b.i.d)	Dose Reduction Level 1 (b.i.d)	Dose Reduction Level 2 (b.i.d)
7-9.5	20 mg	10 mg	0 mg
9.6-13.5	30 mg	20 mg	10 mg
13.6-17.5	40 mg	30 mg	20 mg
17.6-20.5	50 mg	40 mg	30 mg
20.6-24.5	60 mg	50 mg	40 mg
24.6-28.5	70 mg	60 mg	50 mg
28.6-32.5	80 mg	70 mg	60 mg
32.6-36.5	90 mg	80 mg	70 mg
36.6-40.5	100 mg	90 mg	80 mg
40.6-43.5	110 mg	100 mg	90 mg

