3.15 Guidelines for Dose Modifications and Toxicity Management for Combination Therapy

If treatment related toxicities occur when dabrafenib is used in combination with trametinib then both treatments should be simultaneously dose reduced, interrupted or discontinued with the exception shown below:

- Dose modification is necessary for only dabrafenib
 - Mild to moderate pyrexia ([Section 3.15.1](#))
 - Uveitis ([Section 3.13.5](#) and [Section 3.14](#))
- Dose modifications are necessary for only trametinib:
 - Retinal vein occlusions (RVO) and retinal pigment epithelial detachment (RPED) ([Section 3.13.5](#))
 - Left ventricular ejection fraction (LVEF) reduction (asymptomatic, [Section 3.12.3.1](#))
 - Pneumonitis and interstitial lung disease (ILD) (grade 4, [Section 3.13.7](#))

The severity of adverse events (AEs) will be graded utilizing the NCI-CTCAE v4.03 ([NCI 2009](#)). Guidelines for dose modifications and interruptions for management of common toxicities associated with dabrafenib are provided in this section.

Trametinib dose reduction for patients enrolled in all parts of the study should follow dose reduction column in the trametinib dosing nomogram in Appendix 2.

Dabrafenib dose reduction should follow the dose reduction column in the dabrafenib dosing nomogram in Appendix 2 provided for patients enrolled in Part C and Part D, as described below

- Dabrafenib dose modification levels in Part C
 - If a subject is dosed at Dose Level 1, and requires dose reduction, treatment must be discontinued
 - If a subject is dosed at Dose Level 2, and requires dose reduction, follow the dose reduction column in dosing nomogram
- Dabrafenib dose modification levels in Part D.
 - Follow dose reduction column in dosing nomogram

Nomograms for each dosing level are provided in [Appendix 2](#).

If a second dose reduction is required, the treatment should be discontinued.

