23.6- 30	20	1.0	15	0.75
30.1-35	25	1.25	17.5	0.875
35.1- 45	30	1.5	20	1.0
45.1- 60	40	2	30	1.5
60.1- 69.9	40	2	30	1.5
≥70	40	2	30	1.5

*weight measured within 7 days of the start of the cycle

	DOSE LEVEL: 0.032 mg/kg/dose SUBJECT WEIGHT: < 15 kg FORMULATION: TRAMETINIB 0.05 MG/ML ORAL SOLUTION [At this dose level, the 0.05 mg/mL oral solution will be administered to all patients ≤14.9 kg]		
Actual weight* (kg)	Dose		Dose Reduction
	mL	mg	
2-2.4	1.4	0.07	Please refer to 0.025 mg/kg dosing nomogram ('Dose' column)
2.5-3	1.8	0.09	
3.1-3.7	2.2	0.11	
3.8-4.5	2.7	0.13	
4.6-5.5	3.2	0.16	
5.6-6.7	3.9	0.20	
6.8-8.1	4.8	0.24	
8.2-9.8	5.8	0.29	
9.9-11.9	7.0	0.35	
12-13.9	8.3	0.41	
14-14.9	9.2	0.46	

*weight measured within 7 days of the start of the cycle

	DOSE LEVEL: 0.032 mg/kg/dose SUBJECT WEIGHT: ≥ 15 kg FORMULATION: TRAMETINIB 0.05 MG/ML ORAL SOLUTION		
Actual weight* (kg)	Dose		Dose Reduction
	mL	mg	
15-17.9	10.5	0.53	Please refer to 0.025 mg/kg dosing nomogram ('Dose' column)
18-21.5	12.6	0.63	
21.6-25.9	15.2	0.76	
26-31.2	18.3	0.92	
31.3-37.5	22.0	1.10	
37.6-45.1	26.5	1.32	
45.2-54.3	31.8	1.59	
54.4-60	36.6	1.83	
>60	40.0	2	

*weight measured within 7 days of the start of the cycle

Dose and treatment schedule for trametinib tablets for subjects less than 6 years and weight greater or equal to 26kg (0.032 mg/kg/day)

Weight	Dose	Frequency and/or Regimen	Total Daily Dose	Pharmaceutical form and route of administration
26-39.5	2 × 0.5 mg	q.d	1 mg	Tablets for oral administration
39.6-54.5 kg	3 × 0.5 mg	q.d	1.5 mg	Tablets for oral administration
≥ 54.6 kg	1 × 2 mg	q.d	2 mg	Tablets for oral administration

Dose and treatment schedule for trametinib tablets for subjects greater or equal to 6 years and weight greater or equal to 33kg (0.025 mg/kg/day)

Weight	Dose	Frequency and/or Regimen	Total Daily Dose	Pharmaceutical form and route of administration
33-49.5 kg	2 × 0.5 mg	q.d	1 mg	Tablets for oral administration
49.6-69.5 kg	3 × 0.5 mg	q.d	1.5 mg	Tablets for oral administration
≥ 69.6 kg	1 × 2 mg	q.d	2 mg	Tablets for oral administration

Dosing Nomogram – Dabrafenib

1. If a patient's current weight is not a whole number, it should be rounded to its nearest whole number (eg. 12.1 - 12.4 kg is rounded down to 12 and 12.5 – 12.9 is rounded up to 13)
2. Age for daily dose determination in any period during the study is based on the age at enrolment and will remain constant throughout the study.

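### In Appendix 2 the only permitted trametinib dose reduction from the 0.032 mg/kg solution is 1.3% at 24.6-25.9 kg and 4.8% at 16.6-17.9 kg, because it borrows a table with different weight bands

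*Protocol*

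**What the plan says.** Protocol Appendix 2 (15.2) has two solution tables for the 0.032 mg/kg level, below 15 kg and from 15 kg. Both give a volume and a dose by weight; two of the rows read "15-17.9 10.5 0.53" and "21.6-25.9 15.2 0.76" (kg, mL, mg). Neither table has reduced doses of its own. The Dose Reduction column refers the reader elsewhere: "Please refer to 0.025 mg/kg dosing nomogram ('Dose' column".

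Other sections give that column its force:

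- Section 3.15: "Trametinib dose reduction for patients enrolled in all parts of the study should follow dose reduction column" of the trametinib nomogram.
- Section 3.13: "A maximum of one trametinib dose reduction is allowed. If a second dose level reduction is required, treatment will be permanently discontinued".
- Section 3.12.3.1, Table 3-5, after an asymptomatic LVEF fall: "If the event recurs at the reduced dose level, permanently discontinue trametinib".
- Section 3.13.1, Table 3-6: "If the Grade 2 (intolerable) or Grade 3 toxicity recurs while at reduced dose, discontinue study treatment(s").

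**The concern.** A toxicity reduction is meant to lower exposure enough for the child to have a fair chance of continuing. The cross-reference looks as if it steps the child down one level, from 0.032 to 0.025 mg/kg. But both tables give one volume per weight band and their bands do not line up. Where a child sits at the top of a 0.032 band and at the bottom of a 0.025 band, the two volumes almost coincide.

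That child restarts on nearly the same dose after an LVEF fall, a Grade 3 toxicity or an intolerable Grade 2 toxicity. This is the one reduction allowed, so a recurrence then stops treatment. The record would show a failure at the reduced dose although the dose had hardly changed. The same column also sets the restart dose after retinal pigment epithelial detachment (Table 3-10) and pneumonitis (Table 3-11).

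**Working it through.** **Inputs.** All volumes are the printed mL in Appendix 2, for the 0.05 mg/mL solution. The headings of the 0.025 tables did not survive in the text at hand. The tables are identified by their place between the 0.0125 and 0.04 tables and by their doses: 0.5 mg at 20 kg is 0.025 mg/kg.

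**Check of the printed doses.** mg = mL x 0.05. 15.2 x 0.05 = 0.76 mg and 10.5 x 0.05 = 0.525 mg (printed as 0.53). In the 0.025 table, 15 x 0.05 = 0.75 mg and 10 x 0.05 = 0.50 mg. These agree with the protocol, which states no percentage reduction.

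**Formula.** Reduction = 1 - (0.025 volume) / (0.032 volume), for each overlap of a 0.032 band with a 0.025 band. The nominal step is 1 - 0.025/0.032 = 21.9%.

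| Weight (kg) | 0.032 dose (mL) | Reduced to (mL) | Reduction | mg/kg after reduction |
|---|---|---|---|---|
| 3.6-3.7 | 2.2 | 2 | 9.1% | 0.0278-0.0270 |
| 12-12.5 | 8.3 | 5 | 39.8% | 0.0208-0.0200 |
| 12.6-13.9 | 8.3 | 7.5 | 9.6% | 0.0298-0.0270 |
| 15-16.5 | 10.5 | 7.5 | 28.6% | 0.0250-0.0227 |
| 16.6-17.9 | 10.5 | 10 | 4.8% | 0.0301-0.0279 |
| 18-21.5 | 12.6 | 10 | 20.6% | 0.0278-0.0233 |
| 21.6-24.5 | 15.2 | 10 | 34.2% | 0.0231-0.0204 |
| 24.6-25.9 | 15.2 | 15 | 1.3% | 0.0305-0.0290 |

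By the rounded mg column, the 16.6-17.9 kg figure is 1 - 0.50/0.53 = 5.7%.

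**Before and after.** At 24.6 kg the dose is 0.76/24.6 = 0.0309 mg/kg before and 0.75/24.6 = 0.0305 after. At 16.6 kg it is 0.525/16.6 = 0.0316 before and 0.50/16.6 = 0.0301 after.

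**How much of the weight range.** From 10 to 25.9 kg in 0.1 kg steps there are 160 weights. The bands 12.6-13.9, 16.6-17.9 and 24.6-25.9 kg hold 14 each. So 42/160 = 26% get a cut below 10%, and 28/160 = 17.5% get a cut below 5% (by mL).

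**Comparison with the other solution tables.** The 0.0125, 0.025 and 0.04 tables print 31 + 15 + 15 = 61 reduced volumes. By mL, every one is a cut of 20.0% to 33.3% (for example 1 to 0.8 mL and 6 to 4 mL). The formulation therefore does not force the small steps.

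**The case against.** The strongest reply is that the rule does what it intends. It moves the child down one dose level, to the volume any child of that weight receives at 0.025 mg/kg, a level Amendment 5 reports as tolerable. Nothing is miscalculated, because no percentage is promised. The second half of that stands: this is a mismatch between two tables, and a reader who infers an arithmetic error goes further than the text. The first half fails in the affected bands, where the child stays at about 0.027-0.030 mg/kg and the toxicity arose at almost the same dose.

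Second, the percentage is not the only safeguard. For LVEF, trametinib is held until recovery, the echocardiogram is repeated at 2, 4, 8 and 12 weeks after restart, and recurrence stops the drug. That limits the danger. It does not restore the lost chance of continuing on a lower dose.

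Third, the reach is narrow. The two worst bands are about 1.3 kg wide, and at 26 kg the cut is back to 18.0% (18.3 to 15 mL). This also stands. A reader might infer that many children were under-reduced, or that some were harmed; the protocol gives no counts by weight and does not support either. Nor does it state outright that 0.032 was adopted. Part A grew from 38 patients in March 2017 to 50 in July 2020, which equals the full extension of 12. Section 3.2.6 would have stopped enrolment at six or fewer had the dose failed. That suggests 0.032 was used but does not prove it.

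The same overlap makes a Part B escalation almost nil at 24.6-25.9 kg (15 to 15.2 mL, +1.3%). That step is optional ("trametinib dose level may be increased up to 0.032 mg/kg/day if this dose is found to be tolerated in Part A extension"), so the point does not rest on it.

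**Conclusion.** Wrong as written, and worth correcting. At weights plausible for children under 6, the mandatory single reduction from the 0.032 mg/kg solution is 1.3% at 24.6-25.9 kg, 4.8% at 16.6-17.9 kg (5.7% by rounded mg), 9.6% at 12.6-13.9 kg and 9.1% at 3.6-3.7 kg, against a nominal 21.9%. Below 26 kg the 0.032 level has no tablet schedule, so the solution is the only scheduled form.

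This rests on the printed volumes, on the identification of the 0.025 tables given above, and on children actually being treated at 0.032. It concerns the management of individual children and how a discontinuation at the reduced dose is read. It does not show that the recommended dose or the response analyses are wrong. Enrolment is closed. At July 2020, 80 of 139 treated patients had discontinued and 13 had entered the rollover study, so the column matters for those still on treatment at this level.

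**What to change.** Define the reduced dose for the 0.032 solution as the lower of the 0.025 nomogram dose and 0.78 x the current mL, rounded to 0.1 mL, and print the result by weight. In the bands at issue:

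- 3.6-3.7 kg: 0.78 x 2.2 = 1.7 mL
- 12.6-13.9 kg: 0.78 x 8.3 = 6.5 mL
- 16.6-17.9 kg: 0.78 x 10.5 = 8.2 mL
- 24.6-25.9 kg: 0.78 x 15.2 = 11.9 mL

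Every weight then falls by at least about 21%, and no reduced dose rises above the present one. A plain 0.78 factor for all rows would be simpler, but it would raise the reduced dose at 72 of the 160 weights from 10 to 25.9 kg (for example 6.5 instead of 5 mL at 12-12.5 kg, and 11.9 instead of 10 mL at 21.6-24.5 kg).

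Check the current dose of any child already reduced from 0.032 in these bands. Where a child stopped for recurrence at the reduced dose, list the actual percentage cut.

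Cost: a small protocol amendment with IRB/IEC approval, as was needed when Amendment 6 updated the Appendix 2 nomogram and when Amendment 8 changed dose-modification rules. No new visits or data are needed. In these bands a reduced child will receive less than a child of the same weight assigned to 0.025 (11.9 against 15 mL at 24.6-25.9 kg). The large cuts in neighbouring bands, such as 39.8% at 12-12.5 kg, stay as they are.

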3. Children < 6 years-old and subjects, regardless of age, with a risk of choking when swallowing capsules will be required to use the dispersible tablet formulation.
4. The investigator or responsible site personnel should instruct the patient and guardians to take or administer the study drug as per protocol (to promote compliance).

Dabrafenib **Capsule** Dosing Nomogram

Dose Level 1 (Starting dose)*					
< 12 year olds			≥ 12 year olds		
Daily dose: 2.63 mg/kg dabrafenib capsule			Daily dose: 2.25 mg/kg dabrafenib capsule		
Body weight (kg)	Capsules/ dose	Total Daily (actual)	Body weight (kg)	Capsules/ dose	Total Daily (actual)
<32	See dispersible tablet for oral suspension nomogram		<38	See dispersible tablet for oral suspension nomogram	
32-47	50 mg	100 mg	38-55	50 mg	100 mg
48-71	75 mg	150 mg	56-83	75 mg	150 mg
72-94	100 mg	200 mg	84-111	100 mg	200 mg
95-118	125 mg	250 mg	112-138	125 mg	250 mg
≥ 119	150 mg	300 mg	≥ 139	150 mg	300 mg

* No dose reduction is allowed for patients on dose level 2.25 or 2.63 mg/kg/day. If a patient requires dose reduction at this level, dabrafenib treatment must be discontinued

Dose Level 2			
< 12 year olds: 5.25 mg/kg dabrafenib capsule			
Dose			Dose Reduction
Body weight (kg)	Capsules/ dose	Total Daily (actual)	Please refer to 4.5 mg/kg dabrafenib capsules dosing nomogram ('Dose' column).
<16	See dispersible tablet for oral suspension nomogram		
16-23	50 mg	100 mg	
24-33	75 mg	150 mg	
34-42	100 mg	200 mg	
43-52	125 mg	250 mg	
≥ 53	150 mg	300 mg	

Dose Level 2			
≥ 12 year olds: 4.5 mg/kg dabrafenib capsule			
Dose			Dose Reduction
Body weight (kg)	Capsules/ dose	Total Daily (actual)	Please refer to 3.75 mg/kg dabrafenib capsules dosing nomogram.
<19	See dispersible tablet for oral suspension nomogram		
19-27	50 mg	100 mg	
28-38	75 mg	150 mg	
39-50	100 mg	200 mg	
51-61	125 mg	250 mg	
≥ 62	150 mg	300 mg	

3.75 mg/kg dabrafenib capsule		
Body weight (kg)	Capsules/ dose	Total Daily (actual)
<26	See dispersible tablet for oral suspension nomogram	
26-33	50 mg	100 mg
34-46	75 mg	150 mg
47-59	100 mg	200 mg
60-73	125 mg	250 mg
≥ 74	150 mg	300 mg

Dabrafenib 10mg Dispersible Tablet for oral (suspension) Dosing Nomogram

Dose and treatment schedule for dabrafenib (DRB436) 10mg dispersible tablets for patients less than 12 years of age (5.25mg/kg/day)

Weight (kg)	Dose	Frequency and/or Regimen	Total Daily Dose	Pharmaceutical form and route of administration
7-9.5	20 mg	b.i.d	40 mg	Dispersible tablet for oral suspension

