9.6-13.5	30 mg	b.i.d	60 mg	Dispersible tablet for oral suspension
13.6-17.5	40 mg	b.i.d	80 mg	Dispersible tablet for oral suspension
17.6-20.5	50 mg	b.i.d	100 mg	Dispersible tablet for oral suspension
20.6-24.5	60 mg	b.i.d	120 mg	Dispersible tablet for oral suspension
24.6-28.5	70 mg	b.i.d	140 mg	Dispersible tablet for oral suspension
28.6-32.5	80 mg	b.i.d	160 mg	Dispersible tablet for oral suspension
32.6-36.5	90 mg	b.i.d	180 mg	Dispersible tablet for oral suspension
36.6-40.5	100 mg	b.i.d.	200 mg	Dispersible tablet for oral suspension

40.6-43.5	110 mg	b.i.d	220 mg	Dispersible tablet for oral suspension
43.6-47.5	120 mg	b.i.d	240 mg	Dispersible tablet for oral suspension
47.6-51.5	130 mg	b.i.d	260 mg	Dispersible tablet for oral suspension
51.6-55.5	140 mg	b.i.d.	280 mg	Dispersible tablet for oral suspension
≥55.6 kg	150 mg	b.i.d	300 mg	Dispersible tablet for oral suspension

Dose and treatment schedule for dabrafenib (DRB436) 10mg dispersible tablet for patients greater than or equal 12 years of age (4.5 mg/kg/day)

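### The dabrafenib rule that rounds x.5 kg up conflicts with the dispersible-tablet weight bands, which place x.5 kg in the lower band

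*Protocol*

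**What the plan says.** Appendix 2 (Section 15.2) opens its dabrafenib part with a numbered list of instructions, placed before both the capsule and the dispersible-tablet tables. Instruction 1 says of a current weight that is not a whole number that "it should be rounded to its nearest whole number". The example beside it takes 12.1 to 12.4 kg down to 12 and says that 12.5 to 12.9 kg "is rounded up to 13", so an exact half-kilogram goes up. Instruction 3 of the same list says that children under 6 years, and anyone at risk of choking on capsules, "will be required to use the dispersible tablet formulation".

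The capsule tables that follow have whole-kilogram bands (for example 16-23 and 24-33 kg at 5.25 mg/kg). The next table is for "10mg dispersible tablets for patients less than 12 years of age (5.25mg/kg/day"). Its first three rows are "7-9.5 20 mg b.i.d 40 mg", "9.6-13.5 30 mg b.i.d 60 mg" and "13.6-17.5 40 mg b.i.d 80 mg", and the pattern continues up to an open band from 55.6 kg. Tables 3-6a and 3-6b in Section 3.13.1, which govern dose modification, use the same kind of band edges.

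**The concern.** The rule and the table treat the same recorded weight differently. A weight of exactly x.5 kg at a band limit is printed as belonging to the lower band, but instruction 1 turns it into the next whole kilogram, which lies in the band above. A site reading the row and a site rounding first can each point to protocol text, and they arrive at different doses.

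Two things make this more than cosmetic. Dispersible tablets are compulsory for children under 6 years (Section 3.11.2 and Appendix 2) and for those under 12 years who weigh less than 16 kg (Section 4.2.2). The step between bands is a fixed 10 mg b.i.d., so it is proportionally largest in these children. Section 3.11.2 also gives limiting dosing variability between subjects as the reason for using a nomogram, and at these weights the nomogram creates some. Because Table 3-6a has the same edges, the row from which a dose reduction starts is ambiguous too.

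**Working it through.** **Inputs.** Rounding rule and example: Appendix 2, dabrafenib instruction 1. Bands under 12 years: Appendix 2, dispersible-tablet table (same edges in Table 3-6a). Bands at 12 years or older: Table 3-6b, because the Appendix 2 table for that age group is cut off in the text available for this check.

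**Step 1: reproduce the protocol's example.** Rounding half up is r = floor(w + 0.5). This gives 12.1 → 12, 12.4 → 12, 12.5 → 13 and 12.9 → 13, as printed.

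**Step 2: look up each weight twice.** For every weight in 0.1 kg steps, the dose was read once at w and once at r. Relative difference = (dose at r ÷ dose at w) − 1. Daily dose per kg = 2 × b.i.d. dose ÷ w.

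Under 12 years, selected edges:

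| Weight (kg) | By printed row | Rounded weight | By rounded weight | Difference | mg/kg/day, row vs rounded |
|---|---|---|---|---|---|
| 9.5 | 20 mg b.i.d. | 10 | 30 mg b.i.d. | 30/20 − 1 = +50% | 4.21 vs 6.32 |
| 13.5 | 30 mg b.i.d. | 14 | 40 mg b.i.d. | 40/30 − 1 = +33% | 4.44 vs 5.93 |
| 17.5 | 40 mg b.i.d. | 18 | 50 mg b.i.d. | 50/40 − 1 = +25% | 4.57 vs 5.71 |
| 20.5 | 50 mg b.i.d. | 21 | 60 mg b.i.d. | 60/50 − 1 = +20% | 4.88 vs 5.85 |
| 55.5 | 140 mg b.i.d. | 56 | 150 mg b.i.d. | 150/140 − 1 = +7% | 5.05 vs 5.41 |

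The full list of conflicting weights is 9.5, 13.5, 17.5, 20.5, 24.5, 28.5, 32.5, 36.5, 40.5, 43.5, 47.5, 51.5 and 55.5 kg: all 13 closed upper edges, each 10 mg b.i.d. apart.

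At 12 years or older the result is again 13 of 13 edges, from 11.5 kg (20 vs 30 mg b.i.d., +50%) to 64.5 kg (140 vs 150 mg b.i.d., +7%).

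**Step 3: extent.** From 7.0 to 56.0 kg there are 491 weights in 0.1 kg steps, so 13/491 = 2.6%. From 10.0 to 65.0 kg there are 551, so 13/551 = 2.4%. All other weights inside the tables give the same dose either way.

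**Step 4: below the tables.** Weights of 6.5-6.9 kg (under 12 years) and 9.5-9.9 kg (12 years or older) have no row as measured but round into the first band.

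**The case against.** The best counter-argument concerns scope. If instruction 1 governs all dabrafenib dosing, everyone rounds first, each whole kilogram falls in exactly one band, and there is one dose. If it governs capsules only, there is again one dose. On this view the defect is an unstated scope rather than a contradiction. That describes the cause fairly, but it does not remove the conflict. The text never limits the rule to capsules: it stands under the general dabrafenib heading, instruction 3 in the same list names the dispersible tablet, and Section 3.11.2 refers all formulations to the nomogram. If the rule does apply, the printed rows ending at x.5 kg say something it overrides.

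Other points on that side stand, as limits on size:

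- The step comes from the 10 mg tablet. The table itself goes from 20 to 30 mg b.i.d. between 9.5 and 9.6 kg. At 9.5 kg the nominal amount is 5.25 × 9.5 = 49.9 mg/day, and the two candidates, 40 and 60 mg/day, lie about 20% below and 20% above it. Rounding gives 6.32 mg/kg/day at 9.5 kg; the table unrounded already gives 60/9.6 = 6.25 at 9.6 kg.
- The 50% figure belongs to one weight per table, and a patient of 12 years or older at 11.5 kg is unlikely. The case rests on the under-12 table.
- The percentages in step 3 are shares of tabulated weights, not of patients. The protocol gives no weight distribution.
- Amendment 9 reports that all cohorts are closed to enrolment, so what remains is dosing by current weight for patients still on treatment.

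**Conclusion.** The concern holds. Instruction 1 and the dispersible-tablet bands give different doses at all 13 band edges in each age group, by 10 mg b.i.d. each time: +50% at the lowest edge, falling to +7% at the highest. Within the tables the conflict is confined to weights recorded as exactly an edge value, so few dosing decisions are likely to be affected, and nothing here suggests that the trial's conclusions would change. It is a minor point, but it sits in an operative dosing rule and is proportionally largest in the smallest children.

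This assumes that weights are recorded to 0.1 kg and that the rule applies as placed, to dabrafenib in general. The count for 12 years or older further assumes that the Appendix 2 table for that group has the same bands as Table 3-6b; the under-12 result does not depend on it.

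**What to change.** Reconcile instruction 1 with the dispersible-tablet tables. Either state in Appendix 2 whether the rounding rule applies to those tables, or redraw the band edges so that they agree with it, and carry the same wording to Tables 3-6a and 3-6b. The statement should also say how weights just below the first band are handled. Which dose applies at an edge is for the sponsor's clinicians to decide. The cost is one sentence in Appendix 2, plus matching band edges in Section 3.13.1 if that route is taken.
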